KS skin lesions are visibly apparent; the disease can often result in significant psychological problems and social stigma for patients with KS. Symptoms of systemic KS include pain, diarrhea, weight loss, edema, and oral sores. In many cases, KS can severely compromise the QOL by causing physical suffering, scarring, and deformity. Lymphedema, particularly in the face, genitalia, and lower extremities are not uncommon and impair functional ability.¹¹ Survival can often be marked by poor QOL, making it difficult for patients to deal with their disease. While the introduction and use of highly active antiretroviral therapy (HAART) therapy has resulted in a steep decline in the incidence of HIV-related KS with improvements in survival, CRs are rare and the disease remains incurable.^{12,13} Therefore, QOL for patients with KS still remains a major issue. Since QOL has been, and continues to be, such a vital issue in KS, QOL measures have been used as endpoints in AIDS-related KS.¹⁴⁻¹⁶ In a phase II trial with low-dose etoposide, responders had a statistically improvement in pain, physical and bodily pain distress compared to non-responders.¹⁵ In an AIDS Malignancy Consortium (AMC) trial of liposomal doxorubicin versus paclitaxel, two common drugs used in advanced KS, the KS Functional Assessment of HIV Infection (FAHI) QOL instrument with three supplemental questions on pain, swelling and physical appearance was used to collect QOL data.^{17,18} This study was able to show that with treatment, there were significant improvements reported between baseline and treatment values of pain and swelling; these values are of clinical value as this was not captured by the given response values (i.e., complete response, partial response). Clinicians currently take QOL improvement into account when treating KS patients with chemotherapy drugs like liposomal doxorubicin and paclitaxel, which have clear side effects. Therefore, it is also important to consider QOL changes when moving a therapy forward into the clinical arena.

[figure not shown]

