4.0 TREATMENT PLAN

4.1 Agent Administration

Protocol agents will be administered on an outpatient basis. Appropriate dose modifications for sEphB4-HSA are described in [Section 5.0](#). No investigational or commercial agents or therapies other than those described below may be administered with the intent to treat the participant's malignancy.

Each cycle of sEphB4-HSA will be 28 days. sEphB4-HSA is administered intravenously. Each cycle includes administration of 2 doses of sEphB4-HSA intravenously at 10 mg/kg administered on Days 1 and 15. With protocol versions earlier than 4.0, a 15 mg.kg dose level was used as dose level 1, and has been discontinued as discussed in [Section 2.3.8](#).

Study medications will be dispensed at study entry (Day 1) and at each subsequent study visit. sEphB4-HSA will be administered via intravenous infusion at approximately the same time each day.

Whenever possible, Cycle 1 Day 1 should be scheduled on a Monday due to timing of laboratory and biopsy samples. The doses should be calculated prior to or on Day 1 of each cycle; the dose administered should remain the same throughout a cycle but should be recalculated at the start of the next cycle. Doses must be adjusted if a participant's weight has changed more than 10% from baseline or the prior dose. Otherwise, doses may be adjusted in conjunction with institutional guidelines. When holidays or other scheduling conflicts exist, doses may be delayed, ideally no more than 1 day (see [Section 5.6](#) for additional guidance on management of dose interruptions).

If any participant develops major bleeding or any unexpected grade 4 or greater event on study, accrual will be held until the PI and sponsor assess the need for changes to protocol or consent. Dose modifications for other toxicity will be allowed and are described below. Participants requiring a delay of > 28 days (4 weeks) due to drug related toxicity will be removed from the study.

Table 4-A: Standard dosing

Regimen Description – INITIAL DOSE LEVEL					
Agent	Premedications/ Precautions	Dose	Route	Schedule	Cycle Length
sEphB4-HSA	No premedication*	10 mg/kg	I.V. over 1 hour**	Days 1 and 15	28 days (4 weeks)

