4.3 Duration of Therapy

In the absence of treatment delays due to AE(s), treatment may continue for a maximum of 12 cycles or until one of the following criteria listed in [Section 4.5](#) applies. If CR is achieved, the participant will receive one cycle beyond CR. Treatment may be resumed if KS progresses off treatment after a CR, up to a maximum of 12 cycles. The participant will resume the previous dose that he/she was receiving when CR was achieved. Participants who achieve PR or SD may continue the treatment at the dose he/she was receiving when PR or SD was achieved for a maximum of 12 cycles, if the participant and treating physician feel that it is beneficial to continue treatment.

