4.5 Criteria for Removal from Treatment

Participants will be removed from study treatment when any of the criteria listed in [Section 5.0](#) and below applies. The reason for study treatment removal and the date of the participant's last treatment must be documented in the Off Protocol Treatment Form in Advantage eClinical. The date the participant was removed from study treatment must be documented in the source.

- Uncontrolled sustained hypertension, which will be defined as systolic BP > 140, and diastolic BP > 90, even with use of antihypertensive medications.
- Disease progression after completing 2 or more cycles (or at least after 4 doses of sEphB4-HSA).
- Dose delay of more than 28 days.
- Rapid progression of disease that is deemed to be life-threatening.
- Intercurrent illness that prevents further administration of treatment.
- Any participant who develops Multicentric Castleman's disease or a life-threatening systemic inflammatory syndrome will not receive further sEphB4-HSA and will be managed using the best judgment of the treating physician.
 - **These events require mandatory notification of a study chair within 24 hours which will result in immediate notification of all participating sites and a conference call to assess the safety of continued enrollment.**
- Participants who experience Steven-Johnson Syndrome or major allergic reaction.
- Participants who become pregnant or need to breast-feed.
- Participants who require systemic chemotherapy for the treatment of a malignancy other than KS.
- Participants who are noncompliant with respect to taking drugs, keeping appointments, or having tests required for the evaluation of drug safety and efficacy.
- Participants have the right to withdraw from the study at any time for any reason.

- The Investigator has the right to remove participants from the study for clinical reasons which he/she believes are life-threatening to the participant even if such reasons do not fall into the toxicity classifications discussed in [Section 5.0](#).
- General or specific changes in the participant's condition render the participant unacceptable for further treatment in the judgment of the investigator.
- Unacceptable AE(s).

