- 8.2.2.10 Biologic endpoints: peripheral blood for biologic endpoints described in [Appendices I](#) and [III](#) will be collected at Day 1 of Cycles 2, 4, 6, 7, and 10. The samples include blood for immune studies on Day 1 of Cycles 2, 4, and 6 to be done before study treatment dosing. Given this will be a fresh blood sent at room temperature overnight, if the blood for immune studies cannot be collected on Monday-Wednesday (i.e., the dose is administered on Thursday or Friday), this blood work can be obtained the Monday AFTER the dose was given. Blood for HHV-8 viral loads and archived research purposes on Day 1 of Cycles 4, 7, and 10, and at treatment discontinuation.
- 8.2.2.11 Biologic endpoints: peripheral blood for pharmacokinetics as described in [Appendices I](#) and [II](#) will be collected on Day 1 and 15 of Cycle 2; the samples will be drawn pre-dose.
- 8.2.2.12 If HIV positive, T-lymphocyte subsets (CD4 and CD8) to be done every three cycles (Day 1 of Cycle 4, 7, and 10), and at treatment discontinuation.
- 8.2.2.13 If HIV positive, HIV-1 plasma RNA to be done every three cycles (Day 1 of Cycles 4, 7, and 10), and at treatment discontinuation).
- 8.2.2.14 FAHI+KS quality of life questionnaire on Day 15 of Cycle 4 (questionnaire may be performed up until Day 15 of Cycle 5). Those who have HIV-negative KS will not have the HIV portion scored. See [Appendix XII](#) for KAH1+KA questionnaire.

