10.5 Analysis of Exploratory Endpoints

Using the FAHI+KS questionnaire, pain and swelling improved in AIDS-KS patients treated with paclitaxel or pegylated liposomal doxorubicin on AMC009/ECOG E1D96 protocol.¹⁸ Significant improvements in social well-being and cognitive functioning were also reported. Thus, there is an interest in assessing QOL changes after baseline in this study using the same instrument to facilitate comparisons with the previous study.

In the FAHI+KS questionnaire, 5 measures of overall QOL will be scored: physical well-being, emotional well-being, functional and global well-being, social well-being, and

cognitive functioning. The questionnaire will be collected at baseline, cycle 4, and end of treatment. General estimating equations will be used to evaluate changes in the 5 measures of overall QOL over time adjusting for intra-participant variation. There are three supplemental statements regarding participant perception of KS-specific symptoms: pain, swelling. Agreement with each of these statements is graded using a Likert scale from 0 to 4. Responses to these statements may be dichotomized to reflect positive or negative impact of these symptoms. General estimating equations using a log-binomial model will be used to assess changes in these symptoms over time.

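### The QOL GEE in Section 10.5 has no small-sample correction for about 20 participants, so its standard errors run slightly too small; the Cycle 4 estimate should also be labelled as on-treatment

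*Combined protocol and SAP*

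**What the plan says.** Section 10.5 of the combined protocol and SAP plans the analysis of the five FAHI scores in one sentence: "General estimating equations will be used to evaluate changes in the 5 measures of overall QOL over time adjusting for intra-participant variation". For the dichotomised KS symptom items it adds: "General estimating equations using a log-binomial model will be used to assess changes in these symptoms over time". It names no working correlation, variance estimator, small-sample correction, handling of missing questionnaires or significance level for QOL. Section 10.2 sets the sample at 20.

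On timing, Section 10.5 states: "The questionnaire will be collected at baseline, cycle 4, and end of treatment". Section 8.2.2 gives the on-treatment assessment after baseline as "FAHI+KS quality of life questionnaire on Day 15 of Cycle 4 (questionnaire may be performed up until Day 15 of Cycle 5". Section 4.1 fixes the cycle length: "Each cycle of sEphB4-HSA will be 28 days". Among the reasons for stopping treatment, Section 4.5 lists "Disease progression after completing 2 or more cycles (or at least after 4 doses of sEphB4-HSA". Section 8.4 puts a further FAHI+KS at the post-treatment visit, which every participant is due 4-6 weeks after Day 28 of the final cycle.

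The objective in Section 1.3 is exploratory and concerns QOL changes in participants while they are on treatment.

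**The concern.** The usual sandwich variance is justified by a large number of independent participants. With about 20 it tends to be too small, and comparing the ratio with a normal distribution adds to the error. Intervals come out too narrow, and chance changes look significant more often than stated. In a single-arm study the before-after change is the only QOL evidence, and Section 10.5 intends to set it beside an earlier trial that used the same instrument.

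The second issue is who contributes at Cycle 4. Progression can end treatment from about week 8, so some participants have no Cycle 4 score. If their QOL changed less favourably, the Cycle 4 mean is higher than the mean for all treated participants. Section 2.1 gives some reason to think so, citing an earlier trial in which "responders had a statistically improvement in pain, physical and bodily pain distress compared to non-responders".

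**Working it through.** **The plan's own figures.** Section 10.5 states no operating characteristic for QOL. The only ones in the plan belong to the primary design in Section 10.2, and they reproduce with response and toxicity taken as independent:
- Power = P(X≥9 | 20, 0.6) × P(T≤3 | 20, 0.1) = 0.9435 × 0.8670 = 0.818 (stated 0.82).
- Worst-case error = the larger of P(X≥9 | 20, 0.3) = 0.1133 and P(T≤3 | 20, 0.3) = 0.1071 (stated 0.11).

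**Standard errors: closed form, complete data.** With n = 20, time as a category and independence working correlation, the estimated change is the mean paired difference. The sandwich variance is the sum of squared deviations divided by n². It therefore uses n where the unbiased variance uses n−1.
- Usual sandwich with z: reject when |t₁₉| > 1.96 × √(19/20) = 1.910, which has probability 7.1%.
- Mancl-DeRouen with t₁₉: reject when |t₁₉| > 2.093 × √(20/19) = 2.147, which has probability 4.5%.
- Relative interval width: (20/19) × (2.093/1.96) = 1.053 × 1.068 = 1.12, so about 12% wider.

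**Standard errors: simulation, including missing Cycle 4 scores.** Assumptions: Gaussian scores at three times, within-person correlation 0.5, n = 20, 4,000 replicates, no true change, and missingness unrelated to QOL. The post-treatment score is present for all; q is the share without a Cycle 4 score. Monte Carlo error on the rejection rates is about 0.4 points.

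| q | Working correlation | Mean SE / true SD | Usual sandwich, z | Mancl-DeRouen, t |
|---|---|---|---|---|
| 0 | independence | 0.957 | 7.3% | 4.8% |
| 0 | exchangeable | 0.952 | 7.1% | 4.8% |
| 0.25 | independence | 0.971 | 6.7% | 3.4% |
| 0.25 | exchangeable | 0.949 | 8.2% | 4.5% |
| 0.50 | independence | 0.945 | 7.6% | 2.7% |
| 0.50 | exchangeable | 0.923 | 9.0% | 3.8% |

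The usual errors are 3-8% too small. Rejection is 6.7-9.0% before correction and 2.7-4.8% after it. The t degrees of freedom were the number of Cycle 4 completers minus one.

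**Timing, counted from first dose.**
- Cycle 4 Day 15: 3×28 + 14 = 98 days, week 14.
- Cycle 5 Day 15: 4×28 + 14 = 126 days, week 18.
- End of Cycle 2: 56 days, week 8.
- Post-treatment visit: weeks 12-14 for someone stopped after Cycle 2 (8+4 to 8+6), and weeks 16-18 after Cycle 3 (12+4 to 12+6).

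**On-treatment mean against all-treated mean.** Let a share q have no Cycle 4 score, and let their true change be worse by δ (in SD). The all-treated mean is the completers' mean minus qδ, so the completers' mean is too high by qδ. The documents give neither q nor δ, so these are assumptions:
- δ = 0: no bias at any q.
- δ = 0.3 to 0.8 and q = 0.20 to 0.50: from 0.20×0.3 = 0.06 SD to 0.50×0.8 = 0.40 SD.
- With the post-treatment score in the model and an exchangeable correlation, the simulated bias over the same range is about 0.04 to 0.28 SD. At q = 0.35 and δ = 0.5 it falls from 0.175 to about 0.12 SD: reduced by roughly a third, not removed.

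**The case against.** The endpoint is exploratory, Section 10.5 sets no QOL significance level, and the primary design itself accepts 0.11. A few points of excess rejection change no decision. That stands, and it keeps the severity low. The absence of a correction is also read from silence: an analyst could apply one without being told to. That is a reason to write it down.

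A reader might go further and infer that the Cycle 4 analysis does overstate improvement. The documents do not support this as a finding, for four reasons:
- The objective is worded for participants on treatment, so the completers' mean is arguably what is wanted.
- Section 2.2 says response and QOL do not track each other consistently, and that patients can gain QOL without an objective response. Stable participants may also stay on treatment, so non-responders are not the same group as leavers.
- Early complete responders can miss Cycle 4 too: "If CR is achieved, the participant will receive one cycle beyond CR". The offset is probably small, since Section 2.1 calls complete responses uncommon.
- Early leavers are not lost to the QOL analysis. They are due a post-treatment score at nearly the same calendar time.

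The opposite reading, that there is no issue, also goes too far. Progression as defined in Section 9.1.5 includes oedema that limits normal activity, which the KS items touch on directly, so a worse course in leavers is plausible.

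Inverse-probability weighting by response category may look like the remedy. Progressors have essentially no chance of a Cycle 4 score, so stable participants would stand in for them. Take 60% responders at +1 SD, 20% stable at 0 and 20% progressing at −0.5 SD, with all progressors gone. The true mean is 0.60 + 0 − 0.10 = 0.50 SD; the weighted estimate is 0.60×1 + 0.40×0 = 0.60 SD, still 20% too high.

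**Conclusion.** The small-sample point holds. With about 20 participants and no correction, the standard errors for the five QOL scores are about 3-8% too small, and a nominal 5% test rejects about 7-9% of the time. This rests on Gaussian scores, a within-person correlation of 0.5, and the usual sandwich with a normal reference being what is run. The complete-data case also follows in closed form for independence working correlation. The figures do not cover the log-binomial model for the KS items.

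The dropout point holds only conditionally. The Cycle 4 estimate describes those on treatment at weeks 14-18. It exceeds the all-treated change only if leavers do worse, by an amount the plan gives no means of estimating. Severity is low on both counts.

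**What to change.** In Section 10.5:
1. State that standard errors and intervals for the GEE of the five scores will use the bias-reduced (Mancl-DeRouen) sandwich with a t reference distribution, and name the working correlation.
2. Label the Cycle 4 estimate as applying to participants on treatment at that time. Report how many completed each questionnaire and why others did not.
3. Add a sensitivity analysis that brings in the post-treatment FAHI+KS for those without a Cycle 4 score. Say in the report that it reduces possible dropout bias without removing it.
4. Do not add response-category weights.

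Section 10.5 should also match the schedule. It refers to an end-of-treatment questionnaire, whereas the discontinuation list in Section 8.3 has none and Section 8.4 places it at the post-treatment visit.

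The cost is a few sentences and a few lines of code, with no new data collection. The downside is wider intervals, about 12% with complete data, and a test that can be somewhat conservative (2.7% in the worst simulated case) when many Cycle 4 scores are missing.

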10.2 Sample Size/Accrual Rate

A total of 20 evaluable participants will be enrolled. The design was developed by considering the joint probability of clinical response and toxicity simultaneously (Jin H. Alternative designs of phase II trials considering response and toxicity, *Contemp Clin Trials* 28 (2007): 525-53). The null hypothesis for defining the unacceptable region based on clinical response rate and toxicity rate simultaneously and the alternative hypothesis for defining the region for a promising agent are as follows:

- $H_0: P_{\text{resp}} \leq 0.30 \text{ OR } P_{\text{tox}} \geq 0.30$
- $H_1: P_{\text{resp}} \geq 0.60 \text{ AND } P_{\text{tox}} \leq 0.10$

In a single stage design, 20 participants will be evaluated for clinical response and toxicity. Toxicity will be defined as: unacceptable toxicities as defined in [Section 10.1](#). All unacceptable toxicities that are possibly, probably, or definitely attributed to protocol therapy will be counted as a toxicity.

The null hypothesis will be rejected if there are at least 9 responders, and no more than 3 participants who experience unacceptable toxicities. This design has power of 0.82 and a significance level of 0.11. The planned accrual rate will be one participant per month.

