Please circle or mark one number per line to indicate your response as it applies to the past 7 days.

SOCIAL WELL-BEING		Not at all	A little bit	Some- what	Quite a bit	Very much
GS1	I feel close to my friends	0	1	2	3	4
GS2	I get emotional support from my family	0	1	2	3	4
GS3	I get support from my friends	0	1	2	3	4
GS4	My family has accepted my illness	0	1	2	3	4
GS5	I am satisfied with family communication about my illness	0	1	2	3	4
GS6	I feel close to my partner (or the person who is my main support)	0	1	2	3	4
HI3	I have people to help me if I need it	0	1	2	3	4
Q1	Regardless of your current level of sexual activity, please answer the following question. If you prefer not to answer it, please mark this box  and go to the next section.					
GS7	I am satisfied with my sex life	0	1	2	3	4

COGNITIVE FUNCTIONING		Not at all	A little bit	Some- what	Quite a bit	Very much
L1	My thinking is clear	0	1	2	3	4
H18	I have trouble concentrating	0	1	2	3	4
H19	I have trouble remembering things	0	1	2	3	4

ADDITIONAL QUESTIONS RELATED TO KAPOSI SARCOMA		Not at all	A little bit	Some- what	Quite a bit	Very much
1	Pain has interfered with my normal work or activities	0	1	2	3	4
2	I am satisfied with my physical appearance	0	1	2	3	4
3	I have had swelling in my face, arms or legs	0	1	2	3	4

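### Section 10.5 gives the 0–4 Kaposi sarcoma (KS) symptom items only a log-binomial analysis, which forces an unspecified positive/negative cut and discards information in at most 20 participants (minor, exploratory)

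*Combined protocol and SAP*

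**What the plan says.** Section 10.5 introduces the KS items thus: "There are three supplemental statements regarding participant perception of KS-specific symptoms: pain, swelling". It announces three but names two. Section 2.6 and Appendix XII show that the third is physical appearance. On scoring, section 10.5 says "Agreement with each of these statements is graded using a Likert scale from 0 to 4". On analysis it says "Responses to these statements may be dichotomized to reflect positive or negative impact of these symptoms", and then "General estimating equations using a log-binomial model will be used to assess changes in these symptoms over time".

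No cut-point appears in section 10.5 or in Appendix XII. In the appendix, agreement with the pain item or the swelling item ("I have had swelling in my face, arms or legs") is unfavourable. Agreement with the appearance item means satisfaction, so it is favourable.

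The same section analyses the five FAHI measures by GEE and mentions no cut. The questionnaire is given at baseline, cycle 4 and end of treatment. Section 1.3 makes the objective exploratory. On numbers, section 10.2 says "A total of 20 evaluable participants will be enrolled", and section 3.3.1 gives a minimum of 6 and a maximum of 20.

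**The concern.** The wording on dichotomising is permissive, but the wording on the model is not. A log-binomial model cannot take a five-level outcome, and no other model is named for these items, so the stated analysis requires the cut.

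Three things follow.

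- **Lost information.** A participant who moves from 4 to 2 counts as unchanged if both scores fall on the same side of the cut.
- **An open choice.** There are three items and several possible cuts, and appearance runs the other way. What counts as a positive impact could be settled after the data are seen.
- **Fragile estimation.** If nobody has the modelled event at a visit, the log risk ratio for that visit does not exist.

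Sections 2.1 and 2.2 present symptom change as something the response categories can miss. These items carry the KS-specific part of that question, so an insensitive analysis works against the reason for collecting them.

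**Working it through.** **1. The plan's own figure.** Section 10.2 says "The null hypothesis will be rejected if there are at least 9 responders, and no more than 3 participants who experience unacceptable toxicities" and "This design has power of 0.82 and a significance level of 0.11". With response and toxicity independent:

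- Power = P(X ≥ 9 | 20, 0.60) × P(Y ≤ 3 | 20, 0.10) = 0.943 × 0.867 = 0.818, against 0.82 stated.
- Worst-case significance level: P(X ≥ 9 | 20, 0.30) = 0.113 for response and P(Y ≤ 3 | 20, 0.30) = 0.107 for toxicity. Both are 0.11 to two decimals.

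So n = 20 reproduces. It was sized for the joint response and toxicity endpoint and says nothing about the KS items.

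**2. Inputs for the KS items.** The documents supply n ≤ 20 and the 0–4 scale. They give no effect size, baseline distribution, within-person correlation, cut, significance level or power. The following are assumed: 20 pairs, latent normal scores rounded to 0–4, correlation 0.5, two-sided 5%, cuts at ≥1, ≥2 or ≥3.

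**3. Tests compared.**

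- Score: t = mean(d) / (SD(d)/√n), with d the within-person change.
- Dichotomised: log RR = log(p₁/p₀), with robust variance (1/n²) Σ[(vᵢ − p₁)/p₁ − (uᵢ − p₀)/p₀]². Here uᵢ and vᵢ are the indicators before and after, and |z| is compared with 1.96.

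**4. Power, with the best of the three cuts.** Where powers are ranges, the loss runs from lowest score power minus highest log-binomial power to the reverse.

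| Shift | Latent baseline mean | Score | Log-binomial | Loss (points) |
|---|---|---|---|---|
| 0.5 SD | 0.5 | 0.36 | 0.27 | 9 |
| 0.5 SD | 1.5–2.5 | 0.47–0.51 | 0.28–0.29 | 18–23 |
| 0.65 SD | 0.5 | 0.53 | 0.42 | 11 |
| 0.65 SD | 1.5–2.5 | 0.69–0.72 | 0.42–0.45 | 24–30 |
| 0.8 SD | 0.5 | 0.68 | 0.57 | 11 |
| 0.8 SD | 1.5–2.5 | 0.85–0.88 | 0.58–0.62 | 23–30 |

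At 0.3 SD the loss is about 4 points with the low baseline. With a baseline spread evenly over the five levels and a cut at ≥2 it is 8 (21% against 13%).

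**5. Wider grid.** Four baseline distributions × three correlations (0.3–0.7) × six shifts (0.3–1.2 SD) × three cuts = 216 scenarios at n = 20.

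- All cuts: loss 3 to 91 points, median 24; 25 or more in 45%.
- Best cut in each of the 72 settings: loss 3 to 36, median 15; 25 or more in 12.5%.
- The dichotomised analysis had lower power in every scenario.

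**6. Three visits, as planned.** A Gaussian GEE on the score was set against a log-binomial GEE (even baseline, correlation 0.5, n = 20, 300 replicates). Over the three cuts the loss was 7–13 points at 0.3 SD, 20–30 at 0.5 SD and 20–27 at 0.8 SD. Every log-binomial fit converged in these scenarios.

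**7. Estimability.** With latent baseline mean 1.5, cut ≥3 and a 0.65 SD shift, the two-visit log risk ratio was undefined in 37% of replicates when symptom presence was modelled, and in 0% when absence was. The worst grid cases reached 33% at cut ≥2 and 67% over all cuts.

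**The case against.** The strongest defence is that this is descriptive work. No hypothesis, significance level, power or decision attaches to these items, so power is a weak yardstick. That stands and sets the severity. It does not supply the missing cut or direction.

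A second defence is comparability. Sections 2.6 and 10.5 justify the instrument by comparison with the earlier randomised trial of paclitaxel against liposomal doxorubicin, and a proportion may be what is needed. The documents tie that comparison to the questionnaire and do not say that the earlier trial dichotomised. Still, this is a good reason to keep the proportions as a supportive analysis.

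Third, every input to the power figures is assumed. Low baseline scores are plausible, because section 3.2.7 excludes symptomatic KS that impairs function, and low baselines gave the smaller losses. That stands, and it is why ranges are given.

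Fourth, the main comparison uses two visits and the tests are not exactly matched in size. Null rejection was 0.053–0.055 for the score and 0.011–0.051 for the log-binomial test. Conservatism explains part of the loss at extreme cuts. At well-placed cuts the size is near nominal, and the three-visit check shows losses of the same order.

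Two stronger readings are tempting. A reader might infer that the log-binomial model will fail. The documents fix neither the cut, nor the modelled event, nor how time enters, so failure is possible but not established. A reader might also infer that all three items improved in the earlier trial. Sections 2.1, 2.6 and 10.5 report improvement in pain and swelling, not in appearance.

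**Conclusion.** The point holds as a minor one. The only analysis named for three five-level items needs a binary outcome, the cut and its direction are unspecified, and at most 20 participants contribute.

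Under the stated assumptions and with the best cut, the loss is about 4–9 points at 0.3 SD, 9–23 at 0.5 SD and 11–30 at 0.65 to 0.8 SD. It is larger with a badly placed cut.

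A reader might infer a general loss of 25 points or more. That is not supported: the loss was under 25 points in about 55% of the 216 scenarios, and in 87.5% of settings when the best cut was used. The direction is firm; the size depends on inputs that the plan does not state.

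The sample size, the primary analysis and the trial's decision rule are untouched.

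**What to change.** In section 10.5:

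- Name all three items: pain, swelling and physical appearance. Reverse-score appearance (4 minus the response), so that a higher score is worse on every item.
- Analyse each item on its 0–4 scale over the planned assessments with a repeated-measures linear or ordinal GEE, as the main exploratory analysis.
- Keep the dichotomised proportions as a supportive or descriptive analysis for comparison with the earlier trial. Fix the cut for each item in advance. If the log-binomial model is kept for this, state which event is modelled.

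The cost is wording, with no new data or visits. The one drawback is that a mean or ordinal change is slightly less direct to read than a proportion, and the retained proportions cover that.
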